### **6.3. Secondary Efficacy Endpoints**

#### **6.3.1. Definition of the Secondary Efficacy Endpoints**

##### 6.3.1.1. EU-specific

The key secondary efficacy endpoints are:

##### Induction Studies (Cohorts A and B)

- The proportion of subjects achieving clinical remission by CDAI at Week 10
- The proportion of subjects achieving both clinical remission by PRO2 and endoscopic response (combined into a single endpoint on a patient level) at Week 10

##### Maintenance Study

- The proportion of subjects achieving clinical remission by CDAI at Week 58
- The proportion of subjects achieving sustained clinical remission by PRO2 at Weeks 10 and 58
- The proportion of subjects achieving both clinical remission by PRO2 and endoscopic response (combined into a single endpoint on a patient level) at Week 58
- The proportion of subjects achieving 6-month corticosteroid-free remission by PRO2 at Week 58

Refer to [Table 6-1](#) for the endpoint definitions.

##### 6.3.1.2. Other (non-EU)

The key secondary efficacy endpoints are:

##### Induction Studies (Cohorts A and B)

- The proportion of subjects achieving clinical remission by PRO2 at Week 10

- The proportion of subjects achieving clinical response by CDAI at Week 10

#### Maintenance Study

- The proportion of subjects achieving clinical remission by PRO2 at Week 58
- The proportion of subjects achieving clinical response by CDAI at Week 58
- The proportion of subjects achieving sustained clinical remission by CDAI at Weeks 10 and 58
- The proportion of subjects achieving 6 month corticosteroid-free clinical remission by CDAI at Week 58
- The proportion of subjects achieving sustained clinical remission by PRO2 at Weeks 10 and 58
- The proportion of subjects achieving 6 month corticosteroid-free clinical remission by PRO2 at Week 58

Refer to [Table 6-1](#) for the endpoint definitions.

### **6.3.2. Analysis of the Secondary Efficacy Endpoints**

The same primary statistical analysis method described in Section [6.2.4](#) for testing the primary efficacy endpoints will be utilized for testing the key secondary efficacy endpoints. The secondary efficacy endpoints will be tested in the order of clinical importance and interest and at the significance level as specified in Section [3.5](#).

Bar charts of the proportions of subjects achieving each of the key secondary efficacy endpoint by treatment group with corresponding p-values will be provided.

CCI

[REDACTED]

[REDACTED]

[REDACTED]

**CCI** [Redacted]

**CCI** [Redacted]

[Redacted]

[Redacted]

[Redacted]

[Redacted]

[Redacted]

[Redacted]

[Redacted]

[Redacted]

[Redacted]

[Redacted]

[Redacted]

[Redacted]

[Redacted]

[Redacted]

[Redacted]

[Redacted]

[Redacted]

CCI

[REDACTED]

[REDACTED]

[REDACTED]

- The proportion of subjects achieving both clinical remission by PRO2 and endoscopic response (combined into a single endpoint on a patient level) at Week 10

- CCI [REDACTED]

- CCI [REDACTED]

- CCI [REDACTED]

- CCI [REDACTED]

- CCI [REDACTED]

CCI

- CCI [REDACTED]

- The proportion of subjects achieving both clinical remission by PRO2 and endoscopic response (combined into a single endpoint on a patient level) at Week 58

- CCI [REDACTED]

- CCI [REDACTED]

- CCI [REDACTED]

- CCI [REDACTED]

- CCI [REDACTED]

- CCI [REDACTED]

- CCI [REDACTED]

CCI [REDACTED]

CCI [REDACTED]

[REDACTED] [REDACTED]

[REDACTED]

[REDACTED]

CCI [REDACTED]

[REDACTED]

[REDACTED]

CCI [REDACTED]

CCI [REDACTED]

[REDACTED]

CCI [REDACTED]

[REDACTED]

[REDACTED]

CCI

[REDACTED]

[REDACTED]

[REDACTED]

CCI [REDACTED]

CCI [REDACTED]

CCI [Redacted]

[Redacted]

CCI

[Redacted]

[Redacted]

- [Redacted]
- [Redacted]
- [Redacted]
- [Redacted]
- [Redacted]
- [Redacted]

[Redacted]

- [Redacted]
- [Redacted]
- [Redacted]
- [Redacted]

[Redacted]

CCI [Redacted]

CCI [Redacted]

[Redacted]

- [Redacted]

- [Redacted]

[Redacted]

CCI [Redacted]

[Redacted]

[Redacted]

## 6.5. Cohorts A and B End-of-Induction Analysis

After all subjects from Cohorts A and B have completed the Week 10 visit or have terminated prior to Week 10 (and completed post-treatment assessments, if applicable) and corresponding data entry is complete, an End-of-Induction safety and efficacy analysis will be performed for DMC review including cumulative safety analysis and efficacy analysis on primary endpoints. Gilead blinded statistical programmers will provide the unblinded external statistician, who is independent of Gilead and not a member of Gilead's Study Management Team, with the datasets and programs necessary to complete the analysis. The unblinded external statistician will apply the unblinded treatment codes to the datasets and generate the unblinded analysis results.

Both cohorts will be examined independently by the DMC:

Taking into account data in Cohort A and Cohort B, if ALL the following 4 criteria are met for BOTH cohorts, the DMC may recommend overall study discontinuation.

- 2-sided p-value for filgotinib 200 mg vs placebo comparison is larger than 0.05 on clinical remission by CDAI at Week 10
- 2-sided p-value for filgotinib 100 mg vs placebo comparison is larger than 0.05 on clinical remission by CDAI at Week 10
- 2-sided p-value for filgotinib 200 mg vs placebo comparison is larger than 0.05 on endoscopic response at Week 10
- 2-sided p-value for filgotinib 100 mg vs placebo comparison is larger than 0.05 on endoscopic response at Week 10

If the condition above is not met from either cohort, the DMC may recommend that the study continues without modification.

## 6.6. Change from Protocol-Specified Efficacy Analyses

CCI

• CCI

• CCI

• CCI

- CCI [REDACTED]
  - CCI [REDACTED]
- CCI [REDACTED]

Subgroup analyses as defined for the co-primary endpoints, were added for all secondary endpoints.

## 7. SAFETY ANALYSES

Unless otherwise specified, summaries of safety data will be provided for the Safety Analysis Set for Cohort A Induction Study, Cohort B Induction Study, and Maintenance Study, and will include data collected as specified below:

### Induction Studies (Cohorts A and B)

- No later than 30 days after the last dosing date of Induction Study, for subjects who did not take any study treatment from Maintenance Study, or
- On or before the first dosing date of Maintenance Study, for subjects who took any study treatment in Maintenance Study

### Maintenance Study

- No later than 30 days after the last dosing date of Maintenance Study

#### 7.1. Adverse Events and Deaths

##### 7.1.1. Adverse Event Dictionary

Clinical and laboratory AEs will be coded using a current version of MedDRA. System organ class (SOC), high-level group term (HLGT), high-level term (HLT), preferred term (PT), and lower-level term (LLT) will be provided in the AE dataset.

##### 7.1.2. Adverse Event Severity

The severity of AEs was grade using the modified Common Terminology Criteria for Adverse Events (CTCAE), version 4.03. For each episode, the highest grade attained should be reported. If a CTCAE criterion does not exist, the adverse events are graded by the investigator as Grade 1, 2, 3, 4, or 5 according to toxicity criteria specified in the protocol. The severity grade of events for which the investigator did not record severity will be categorized as “missing” for tabular summaries and data listings. The missing category will be listed last in the summary presentation.

##### 7.1.3. Relationship of Adverse Events to Study Drug

Related AEs are those for which the investigator selected “Related” on the AE eCRF to the question of “Related to Study Treatment.” Relatedness will always reflect the investigator assessment of causality rather than the sponsor’s. Events for which the investigator did not record relationship to study drug will be considered related to study drug for summary purposes. However, by-subject data listings will show the relationship as missing.

#### 7.1.4. Serious Adverse Events

Serious adverse events (SAEs) will be identified and captured as SAEs if AEs met the definitions of SAE specified in the study protocol. SAEs captured and stored in the clinical database will be reconciled with the safety database before data finalization.

#### 7.1.5. Treatment-Emergent Adverse Events

##### 7.1.5.1. Definition of Treatment-Emergent Adverse Events

Treatment-emergent adverse events (TEAEs) are defined as 1 or both of the following:

##### Induction Studies (Cohorts A and B)

- Any AEs with an onset date on or after the study drug start date for each Induction Study (Day 1) and
  - No later than 30 days after the last dosing date of Induction Study, for subjects who did not take any study treatment from Maintenance Study, or
  - Before the first dosing date of Maintenance Study, for subjects who took any study treatment in Maintenance Study
- Any AEs leading to premature discontinuation of Induction Study drug

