##### Maintenance Study

- Any AEs with an onset date on or after the study drug start date for the Maintenance Study and no later than 30 days after last dosing date of Maintenance Study
- Any AEs leading to premature discontinuation of Maintenance Study drug

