### Induction Studies (Cohorts A and B)

- The AE onset date is the same as or after the month and year (or year) of the first dosing date of study drug, and
- The AE onset date is the same as or before the month and year (or year) of the date corresponding to
  - 30 days after the last dosing date of Induction Study, for subjects who did not take any study treatment in Maintenance Study, or
  - The day before the first dosing date of Maintenance Study, for subjects who took any study treatment in Maintenance Study

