### Maintenance Study

- The AE onset date is the same as or after the month and year (or year) of the first dosing date of Maintenance Study, and
- The AE onset date is the same as or before the month and year (or year) of the date corresponding to 30 days after the last dosing date of Maintenance Study

An AE with completely missing onset and stop dates, or with the onset date missing and a stop date later than the first dosing date of study drug, will be considered to be treatment emergent. In addition, an AE with the onset date missing and an incomplete stop date with the same or later month and year (or year alone if month is not recorded) as the first dosing date of study drug will be considered treatment emergent.

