#### **7.1.6. Summaries of Adverse Events and Deaths**

Treatment-emergent AEs will be summarized based on the Safety Analysis Set for Cohort A Induction Study, Cohort B Induction Study, and Maintenance Study.

No formal statistical testing is planned.

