### 7.2.2.2. Treatment-Emergent Marked Laboratory Abnormalities

#### Induction Studies (Cohorts A and B)

Treatment-emergent marked laboratory abnormalities are defined as values that increase at least 3 toxicity grades from baseline at any postbaseline time point, and

- No later than 30 days after the last dosing date of Induction Study, for subjects who did not take any study treatment from the Maintenance Study, or
- On or before the first dosing date of Maintenance Study, for subjects who took any study treatment in the Maintenance Study

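### The SAP closes the Induction adverse-event window at the first Maintenance dose but not at the first open-label extension dose, so events on open-label filgotinib can be counted as placebo if they are recorded in this study

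*SAP*

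**What the plan says.** **Induction window.** SAP 7.1.5.1 treats an AE as treatment-emergent up to the day before the first Maintenance dose for Maintenance entrants. For all others the limit is "No later than 30 days after the last dosing date of Induction Study, for subjects who did not take any study treatment" in Maintenance. SAP 7.1.5.2 repeats this for partial dates: "30 days after the last dosing date of Induction Study, for subjects who did not take any study treatment in Maintenance Study". SAP 7 has the same two branches for safety data in general, the first being "On or before the first dosing date of Maintenance Study, for subjects who took any study treatment in Maintenance Study". SAP 3.8.1.1 defines the last Induction dosing date by Induction study drug, so LTE drug does not move it. None of these rules mentions the LTE.

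**Maintenance window.** SAP 7.1.5.1 runs to "no later than 30 days after last dosing date of Maintenance Study", again with no LTE cut.

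**Route onto open-label drug.** Protocol 3.4 and 5.3 offer open-label filgotinib in the LTE to Week 10 non-responders from any arm. Protocol 3.6 offers it to Maintenance subjects who meet the disease-worsening criteria. Under protocol 6.5, LTE entrants do not have the 30-day post-treatment visit.

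**Grouping.** SAP 3.2 moves a subject out of the randomized group for safety only if the actual treatment differed for the whole treatment duration. A placebo subject who enters the LTE therefore stays in the placebo group.

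**Recording.** Protocol 7.3.1 asks for all AEs in this study's eCRF until 30 days after the last study drug. It states no exemption for LTE entrants.

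**The concern.** The SAP already closes a window when the subject's next treatment starts, but it does so for only one of the two routes onto new treatment. The other route, into the LTE, is the one that most placebo subjects are expected to qualify for.

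Safety and tolerability is a secondary objective of each study, and its main display is the percentage of subjects with at least one event, by arm (SAP 7.1.6.1). If a placebo non-responder has a first event on open-label filgotinib inside the 30 days and it is entered here, that subject becomes a placebo case. Where filgotinib raises the risk of an event, the error makes the placebo percentage too high and the arms look more alike than they are. For a safety comparison this is the less cautious direction.

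**Working it through.** The plan states no figure for this point, so the check is of the rules first and then of the possible size.

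**1. Following the rules for one subject.** Take a placebo subject who is a non-responder at Week 10 and starts open-label filgotinib in the LTE a few days after the last blinded dose.
- No Maintenance dose was taken, so the second branch applies and the window stays open for 30 days after the last blinded dose.
- The subject remains in the placebo group (SAP 3.2).
- An AE 10 days after the first open-label dose falls inside the window if the gap before that dose was under 20 days. It is then a placebo treatment-emergent AE, provided it is in this study's database.

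**2. How many subjects could follow this route.** Inputs, per cohort: 220 per arm; planned placebo PRO2 remission 15% and endoscopic response 10% (protocol 8.9.1.1); 40% of filgotinib subjects with either response (protocol 8.9.2).
- The 40% reproduces the plan's own count: 0.40 × 2 × 220 = 176 eligible for Maintenance per dose.
- Placebo subjects with either response: at least max(15%, 10%) = 15%, at most 15% + 10% = 25%.
- Placebo non-responders: 0.75 × 220 = 165 to 0.85 × 220 = 187.
- Filgotinib non-responders per arm: 0.60 × 220 = 132.

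**3. Share of placebo window time that could be open-label (illustration).** Week 11 is Day 78, so take the last blinded dose as Day 77. The window is 77 days for responders and 77 + 30 = 107 days for non-responders. Let *p* be placebo non-response, *u* LTE uptake and *g* the gap in days before the first LTE dose. The documents give neither *u* nor *g*; the assumed ranges are 50-100% and 0-14 days, with full capture of AEs and early discontinuations ignored.

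Share = *p·u*·(30 − *g*) / [107*p* + 77(1 − *p*)]

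| Case | Numerator (days per subject) | Denominator | Share | Open-label person-days per 220 |
|---|---|---|---|---|
| *p* = 0.75, *u* = 0.5, *g* = 14 | 6.0 | 99.5 | 6.0% | 220 × 6.0 = 1,320 |
| *p* = 0.85, *u* = 1, *g* = 0 | 25.5 | 102.5 | 24.9% | 220 × 25.5 = 5,610 |

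If non-responders take their last blinded dose on Day 71, the shares are 6.3% and 26.2%. With no capture in this study, the share is zero in every case.

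**4. Maintenance.** The gap has the same form. No disease-worsening rate is given, so it is not sized.

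**5. Against the protocol.** Protocol 8.6 and 8.6.2 give 30 days after the last dose to subjects who stopped early, before or at Week 10, and end at Week 10 for those who completed Week 10 dosing and stayed on study drug.
- If an LTE rollover counts as having stopped at Week 10, the SAP's 30 days agree with the protocol.
- If a rollover counts as having stayed on study drug, the SAP window is up to 107 − 71 = 36 days longer.
- For Maintenance entrants, the SAP window ends about 77 − 71 = 6 days after the protocol's.
- The SAP's Maintenance window follows the protocol's 30 days after permanent discontinuation.

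**The case against.** **The events may not be in this database.** The LTE is a separate study with its own number, reporting under protocol 7.3.1 is subject to instructions not included here, and rollovers have no later scheduled AE visit in this study. This stands as a limit on size: contamination could be nil. It does not remove the point, because the protocol text does not exempt rollovers. If the events are held elsewhere, the 30-day window is not observed for them.

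**The size rests on assumed inputs.** Uptake, gap and capture appear nowhere in the documents, and the upper end needs full uptake, no gap and full capture together. This stands. The 6-25% is a range of possible exposure, not an estimate of bias.

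**The planned statistic is a percentage of subjects.** SAP 7.1.6.1 counts each subject once per summary, and SAP 7.1.6 says "No formal statistical testing is planned". A reader might infer that a true rate ratio would be reported diluted by a calculable factor. The documents do not support that, because these summaries use no person-time rate. A placebo percentage rises only through subjects who had no earlier event of that kind.

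**A reader might infer that the SAP plainly contradicts the protocol, or that rollovers fit no protocol category.** The protocol's wording covers stopping at Week 10 as well as before it, so one reading puts them in the 30-day group. What stands is ambiguity.

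**The fix has a price.** Last dose plus 30 days also catches late effects of blinded drug, and for filgotinib-arm rollovers the open-label drug is the same molecule. This stands, and it is a real trade-off.

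**Conclusion.** The point holds in a limited form. Applied as they read, the SAP's window and grouping rules can assign AEs on open-label filgotinib to placebo, because the cut made for Maintenance entrants is not made for LTE entrants. The fault lies in the end date, not in the grouping rule of SAP 3.2.

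The number of subjects concerned (165 to 187 of 220 placebo subjects per cohort) follows from the planned response rates, before dropout and before any LTE refusal. The share of window time (6-25%) rests on the assumed uptake, gap and capture, and it is zero without capture. The documents do not show that any placebo result is in fact contaminated, and they allow no estimate of how far a reported percentage would move.

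In Maintenance the gap is the same, but there the SAP follows the protocol, so it is a weakness shared by both documents and not a departure by the SAP.

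This is a cheap improvement to descriptive safety tables. It does not affect the efficacy conclusions.

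**What to change.** 1. In SAP 7, 7.1.5.1 and 7.1.5.2, for Induction and Maintenance subjects who enter the LTE on open-label filgotinib, end the AE window at the earlier of last blinded dose plus 30 days and the day before the first open-label LTE dose. Leave Week 58 completers who continue blinded drug unchanged.
2. State where AEs with onset after LTE entry are held, and whether protocol 7.3.1 applies to rollovers.
3. Clarify how protocol 8.6 and 8.6.2 class LTE rollovers: as having stopped by Week 10, or as having stayed on study drug.
4. List the resulting departures in SAP 7.7, which now names only the dropped overall safety analysis. The Maintenance cut would be a new departure and belongs there.

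The same clause could be added to the laboratory rules (SAP 7.2.2.1 and 7.2.2.2), keeping their existing on-or-before form. This is optional: rollovers have no laboratory tests scheduled here after Week 10 except at early termination, so little data is at stake.

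The cost is one clause in each section and one LTE first-dose date merged from the other study. The downside is up to 30 days less counted follow-up per rollover, so late effects of blinded drug in that period would not be counted here.

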##### Maintenance Study

- Any AEs with an onset date on or after the study drug start date for the Maintenance Study and no later than 30 days after last dosing date of Maintenance Study
- Any AEs leading to premature discontinuation of Maintenance Study drug

##### 7.1.5.2. Incomplete Dates

If the onset date of the AE is incomplete and the AE stop date is not prior to the first dosing date of study drug, then the month and year (or year alone if month is not recorded) of onset determine whether an AE is treatment-emergent. For first dosing date and last dosing date defined for Induction Studies (Cohorts A and B) and Maintenance Study, please refer to Section 3.8.1. The event is considered treatment-emergent if both of the following 2 criteria are met:

### Induction Studies (Cohorts A and B)

- The AE onset date is the same as or after the month and year (or year) of the first dosing date of study drug, and
- The AE onset date is the same as or before the month and year (or year) of the date corresponding to
  - 30 days after the last dosing date of Induction Study, for subjects who did not take any study treatment in Maintenance Study, or
  - The day before the first dosing date of Maintenance Study, for subjects who took any study treatment in Maintenance Study

### Maintenance Study

- The AE onset date is the same as or after the month and year (or year) of the first dosing date of Maintenance Study, and
- The AE onset date is the same as or before the month and year (or year) of the date corresponding to 30 days after the last dosing date of Maintenance Study

An AE with completely missing onset and stop dates, or with the onset date missing and a stop date later than the first dosing date of study drug, will be considered to be treatment emergent. In addition, an AE with the onset date missing and an incomplete stop date with the same or later month and year (or year alone if month is not recorded) as the first dosing date of study drug will be considered treatment emergent.

#### **7.1.6. Summaries of Adverse Events and Deaths**

Treatment-emergent AEs will be summarized based on the Safety Analysis Set for Cohort A Induction Study, Cohort B Induction Study, and Maintenance Study.

No formal statistical testing is planned.

##### 7.1.6.1. Summaries of AE Incidence

The number and percentage of subjects who experienced at least 1 TEAE will be provided and summarized by SOC, HLT, PT, and treatment group. For other AEs described below, summaries will be provided by SOC, PT, and treatment group:

- TEAEs of Grade 3 or higher (by maximum severity)
- TEAEs of Grade 2 or higher (by maximum severity)
- All TE treatment-related AEs
- TE treatment-related AEs of Grade 3 or higher (by maximum severity)

- TE treatment-related AEs of Grade 2 or higher (by maximum severity)
- All TE SAEs
- All TE treatment-related SAEs
- All TEAEs leading to premature discontinuation of study drug
- All TEAEs leading to premature discontinuation of study
- All TE SAEs leading to death (ie, outcome of death)
- All TEAEs leading to temporary dose interruption of study drug

A brief, high-level summary of AEs described above will be provided by treatment group presenting the number and percentage of subjects who reported the above AEs. All deaths observed in the study will be also included in this summary.

Multiple events will be counted only once per subject in each summary. Adverse events will be summarized and listed first in alphabetic order of SOC and HLT within each SOC (if applicable), and then by PT in descending order of total frequency within each SOC. In addition, a summary of all AEs occurring at least 2% of subjects will be summarized by SOC and PT in order of descending frequency. For summaries by severity grade, the most severe grade will be used for those AEs that occurred more than once in an individual subject during the study.

In addition, the following tables will be generated and summarized by PT only, in descending order of total frequency:

- TEAEs
- TEAEs of Grade 3 or higher
- TEAEs of Grade 2 or higher
- TE SAEs
- TE treatment-related AEs
- TE treatment-related SAEs
- TEAEs leading to premature discontinuation of study drug

Data listings will be provided for the following:

- All AEs, indicating whether the event is treatment-emergent
- All AEs of Grade 3 or higher
- All AEs of Grade 2 or higher
- SAEs
- Deaths
- All AEs leading to death (ie, outcome of death)
- AEs leading to premature discontinuation of study drug
- AEs leading to premature discontinuation of study
- AEs leading to dose temporary interruption of study drug
- AEs related to COVID-19, as determined by the COVID-19 Standardised MedDRA Query (SMQ) narrow search

In addition, an XML file will be created to support EUDRACT reporting containing serious AEs, non-serious AEs and non-serious AEs occurring in at least 5% of subjects in at least one treatment arm, either at a system organ class level or at PT level (this XML file will be created in-house).

